Principal Investigator **Co/Sub-Investigator** Medical or Psychological Responsible Investigator Student Investigator **Research Coordinator** Research Nurse Consultant **Research Assistant** Pharmacist Statistician Regulatory Coordinator Trainee/Student (i.e. not Student-Investigator) Other N/A: Requesting Waiver of Consent**5. * Describe the consent procedures used for this group. Include when, where, and how consent / assent will be obtained both initially and, if applicable, during ongoing participation in the study:**

Immediately prior to the first intervention session. The basics of the process will be provided over the phone prior to participants being scheduled for the first session.

6. * Describe the process for minimizing coercion to participate:

Participants will have decided based on a phone conversation to participate and will be free to change their minds once they arrive for the session.

7. * How much time will participants be given to make a decision:

We will contact them within a day or two of them screening eligible and the appointment could be several days after that. Once at the in-person meeting, we will ensure they have at least 15 minutes to decide if they need it.

8. If applicable, describe the procedures for consenting children upon entering adulthood or participants who are no longer decisionally impaired:

ID: MS8_HM20011245

View: SF_IRB_ConsentPlan_Groups

Consent Groups

1. * Enter a descriptive name for this consent / assent group:

Screening survey - Aim 2

2. * Select all that apply to this consent / assent group:

Name

- Written/Signed Consent by Participant
- Written/Signed Consent by Parent/Guardian (for child) or Legally Authorized Representative (for adult)
- Written/Signed Consent for Genetic Testing
- Written/signed assent by Child or Decisionally Impaired Adult
- Verbal Assent by Child
- Short Form Consent (limited applicability)
- None of the Above (select waiver below)**

3. * Select any waivers that apply to this consent / assent group:

- No Waivers Requested
- Waiver of Some or All Elements of Consent
- Waiver of Assent by Child or Decisionally Impaired Adult
- Waiver of Parental Permission or Legally Authorized Representative Consent
- Waiver of Documentation of Consent/Assent (not signed)**
- Exception from Informed Consent (for emergency research only)

4. * Select all study team role(s) that will obtain consent / assent from this group:

- Principal Investigator**
- Co/Sub-Investigator**
- Medical or Psychological Responsible Investigator
- Student Investigator
- Research Coordinator**
- Research Nurse
- Consultant
- Research Assistant**

- Pharmacist
- Statistician
- Regulatory Coordinator
- Trainee/Student (i.e. not Student-Investigator)
- Other
- N/A: Requesting Waiver of Consent

5. *** Describe the consent procedures used for this group. Include when, where, and how consent / assent will be obtained both initially and, if applicable, during ongoing participation in the study:**
In community settings where TGW are recruited (e.g., clinics) or online.
6. *** Describe the process for minimizing coercion to participate:**
The incentive is quite modest \$5. We will be friendly rather than coercive in our approach.
7. *** How much time will participants be given to make a decision:**
As much time as is practical which will depend on the setting, the time of day (e.g., if approached right as the clinic opens could be several hours, if approached shortly before the clinic closes could be a shorter period), and how long we will be recruiting in the setting. We will ensure each participant has at least 15 minutes to make a decision.
8. **If applicable, describe the procedures for consenting children upon entering adulthood or participants who are no longer decisionally impaired:**
N/A

ID: MS8_HM20011245

View: SF_IRB_ConsentPlan_Groups

Consent Groups

1. *** Enter a descriptive name for this consent / assent group:**

Aim 1 Qualitative Interview - Key Informants

2. *** Select all that apply to this consent / assent group:**

Name

- Written/Signed Consent by Participant
- Written/Signed Consent by Parent/Guardian (for child) or Legally Authorized Representative (for adult)
- Written/Signed Consent for Genetic Testing
- Written/signed assent by Child or Decisionally Impaired Adult
- Verbal Assent by Child
- Short Form Consent (limited applicability)
- None of the Above (select waiver below)

3. *** Select any waivers that apply to this consent / assent group:**

No Waivers Requested

Waiver of Some or All Elements of Consent

Waiver of Assent by Child or Decisionally Impaired Adult

Waiver of Parental Permission or Legally Authorized Representative Consent

Waiver of Documentation of Consent/Assent (not signed)

Exception from Informed Consent (for emergency research only)

4. * Select all study team role(s) that will obtain consent / assent from this group:

Principal Investigator

Co/Sub-Investigator

Medical or Psychological Responsible Investigator

Student Investigator

Research Coordinator

Research Nurse

Consultant

Research Assistant

Pharmacist

Statistician

Regulatory Coordinator

Trainee/Student (i.e. not Student-Investigator)

Other

N/A: Requesting Waiver of Consent

5. * Describe the consent procedures used for this group. Include when, where, and how consent / assent will be obtained both initially and, if applicable, during ongoing participation in the study:
In person, prior to the interview.

6. * Describe the process for minimizing coercion to participate:

These will be professionals either (a) working with the TGW community or (b) providing economic services to individuals in the area. Interviews will be arranged by phone ahead of time. It's unlikely that such an individual would

feel coerced to participate. They will be free to change their minds once they arrive for the session.

7. * How much time will participants be given to make a decision:

They will be contacted by phone prior to the interview and will be given as much time as they need to make a decision--for example, the in-person interview will be scheduled in the future. Once at the in-person meeting, we will ensure they have at least 15 minutes to decide if they need it.

8. If applicable, describe the procedures for consenting children upon entering adulthood or participants who are no longer decisionally impaired:

ID: MS8_HM20011245

View: SF_IRB_ConsentPlan_Groups

Consent Groups

1. * Enter a descriptive name for this consent / assent group:

Aim 3 intervention

2. * Select all that apply to this consent / assent group:

Name

Written/Signed Consent by Participant

Written/Signed Consent by Parent/Guardian (for child) or Legally Authorized Representative (for adult)

Written/Signed Consent for Genetic Testing

Written/signed assent by Child or Decisionally Impaired Adult

Verbal Assent by Child

Short Form Consent (limited applicability)

None of the Above (select waiver below)

3. * Select any waivers that apply to this consent / assent group:

No Waivers Requested

Waiver of Some or All Elements of Consent

Waiver of Assent by Child or Decisionally Impaired Adult

Waiver of Parental Permission or Legally Authorized Representative Consent

Waiver of Documentation of Consent/Assent (not signed)

Exception from Informed Consent (for emergency research only)

4. * Select all study team role(s) that will obtain consent / assent from this group:

Principal Investigator

Co/Sub-Investigator

Medical or Psychological Responsible Investigator

Student Investigator

Research Coordinator

Research Nurse

Consultant

Research Assistant

Pharmacist

Statistician

Regulatory Coordinator

Trainee/Student (i.e. not Student-Investigator)

Other

N/A: Requesting Waiver of Consent

5. * Describe the consent procedures used for this group. Include when, where, and how consent / assent will be obtained both initially and, if applicable, during ongoing participation in the study:

Immediately prior to the first intervention session. The basics of the process will be provided over the phone prior to participants being scheduled for the first session.

6. * Describe the process for minimizing coercion to participate:

Participants will have decided based on a phone conversation to participate and will be free to change their minds once they arrive for the session.

7. * How much time will participants be given to make a decision:

We will contact them within a day or two of them screening eligible and the appointment could be several days after that. Once at the in-person meeting, we will ensure they have at least 15 minutes to decide if they need it.

8. If applicable, describe the procedures for consenting children upon entering adulthood or participants who are no longer decisionally impaired:

ID: MS8_HM20011245

View: SF_IRB_ConsentPlan_Groups

Consent Groups

1. * Enter a descriptive name for this consent / assent group:

Aim 1 Qualitative Interview - transgender participants (consent form is for both previously vulnerable and currently vulnerable)

2. * Select all that apply to this consent / assent group:

Name

Written/Signed Consent by Participant

Written/Signed Consent by Parent/Guardian (for child) or Legally Authorized Representative (for adult)

Written/Signed Consent for Genetic Testing

Written/signed assent by Child or Decisionally Impaired Adult

Verbal Assent by Child

Short Form Consent (limited applicability)

None of the Above (select waiver below)

3. * Select any waivers that apply to this consent / assent group:

No Waivers Requested

Waiver of Some or All Elements of Consent

Waiver of Assent by Child or Decisionally Impaired Adult

Waiver of Parental Permission or Legally Authorized Representative Consent

Waiver of Documentation of Consent/Assent (not signed)

Exception from Informed Consent (for emergency research only)

4. * Select all study team role(s) that will obtain consent / assent from this group:

Principal Investigator

Co/Sub-Investigator

Medical or Psychological Responsible Investigator

Student Investigator

Research Coordinator

Research Nurse

Consultant

Research Assistant

- Pharmacist
- Statistician
- Regulatory Coordinator
- Trainee/Student (i.e. not Student-Investigator)
- Other
- N/A: Requesting Waiver of Consent

5. * Describe the consent procedures used for this group. Include when, where, and how consent / assent will be obtained both initially and, if applicable, during ongoing participation in the study:

In person, for individuals who screened as eligible. Discussion of the research activities will occur over the phone prior to setting an appointment to meet with the person. Informed consent will occur at the in-person session, generally immediately prior to conducting the interview.

6. * Describe the process for minimizing coercion to participate:

Participants will have decided based on a phone conversation to participate and will be free to change their minds once they arrive for the session.

7. * How much time will participants be given to make a decision:

We will contact them within a day or two of them screening eligible and the appointment could be several days after that. Once at the in-person meeting, we will ensure they have at least 15 minutes to decide if they need it.

8. If applicable, describe the procedures for consenting children upon entering adulthood or participants who are no longer decisionally impaired:

ID: MS8_HM20011245

View: SF_IRB_ConsentPlan_Groups

Consent Groups

1. * Enter a descriptive name for this consent / assent group:

Qualitative interview assessing religious discrimination (conducted during Aim 3)

2. * Select all that apply to this consent / assent group:

Name

- Written/Signed Consent by Participant
- Written/Signed Consent by Parent/Guardian (for child) or Legally Authorized Representative (for adult)
- Written/Signed Consent for Genetic Testing
- Written/signed assent by Child or Decisionally Impaired Adult
- Verbal Assent by Child
- Short Form Consent (limited applicability)
- None of the Above (select waiver below)**

3. * Select any waivers that apply to this consent / assent group:

- No Waivers Requested
- Waiver of Some or All Elements of Consent
- Waiver of Assent by Child or Decisionally Impaired Adult
- Waiver of Parental Permission or Legally Authorized Representative Consent
- Waiver of Documentation of Consent/Accent (not signed)**
- Exception from Informed Consent (for emergency research only)

4. * Select all study team role(s) that will obtain consent / assent from this group:

- Principal Investigator**
- Co/Sub-Investigator**
- Medical or Psychological Responsible Investigator
- Student Investigator
- Research Coordinator**
- Research Nurse
- Consultant
- Research Assistant**
- Pharmacist
- Statistician
- Regulatory Coordinator
- Trainee/Student (i.e. not Student-Investigator)
- Other
- N/A: Requesting Waiver of Consent

5. * Describe the consent procedures used for this group. Include when, where, and how consent / assent will be obtained both initially and, if applicable, during ongoing participation in the study:

In person, for individuals who screened as eligible and indicated interest in participating. Discussion of the research activities will occur over the phone prior to setting an appointment to meet with the person. Informed consent will occur at the in-person session, generally immediately prior to conducting the interview.

6. * Describe the process for minimizing coercion to participate:

Participants will have decided based on a phone conversation to participate and will be free to change their minds once they arrive for the session.

7. * How much time will participants be given to make a decision:

We will contact them within a day or two of them screening eligible and the appointment could be several days after that. Once at the in-person meeting, we will ensure they have at least 15 minutes to decide if they need it.

8. If applicable, describe the procedures for consenting children upon entering adulthood or participants who are no longer decisionally impaired:

N/A

ID: MS8_HM20011245

View: SF_IRB_StudyLocation_NonVCUSitesDetails

Non-VCU Site Details

1. * Name of institution or site:

University of Missouri-St. Louis

2. * Provide a description of the institution's or site's role in the research and what study activities they will be performing:

This is a two site study with equal research activities in community locations in Richmond and St. Louis, MO. [name] at VCU is the lead PI. Investigators at UMSL include [name]., and [name].

All work in Aims 1, 2, and 3, will be conducted equally between both sites.

3. * Describe the adequacy of the institution or site to ensure human participant safety, particularly in event of unanticipated emergency:

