Some trans women who participate will receive the intervention right away. Others will receive it in six months. Who gets it right away versus later is randomly determined. This is so we can test the effects of the intervention.

If you are randomly assigned to receive the intervention right away, you will come to six sessions on six different days. Each session will last for around 2 ♦ hours (around 15 hours total).

If you are randomly assigned to receive the intervention in 6 months, you will come to three sessions on three different days. Each session will last for around 4 hours (around 12 hours total).

Sessions will be held at VCU or at one of our community partners.

Some participants will also receive some financial assistance for finding a job and for gender transition costs. Who receives that financial assistance will be also randomly determined.

We will audio record the intervention, including what you say when you participate, but we will keep everything you tell us confidential. The intervention is expected to last a total of around 15 hours, spread out over 6 days (2 1/2 hours per day). An incentive of \$15/hour will be paid for your participation. So, if you came to 15 hours, you would receive \$225 and if you come to 12 hours, you would receive \$180.

If you participate, you will also be asked to complete a questionnaire four times. The first time you complete it, we will pay you \$20. That amount will go up by \$5 for each additional time you complete the questionnaire -- \$25 for the second time (3 months later), \$30 for the third time (3 months after that), and \$35 the fourth time (3 months after that). If you complete all four questionnaires, we will give you an additional \$50 bonus.

I ♦ m happy to answer any questions you have. Please let me know if you♦d like to learn more or if you♦d like to participate in the intervention.

Regards,

[name]♦

If contacted, the writer will answer any questions and, if the participant is interested, schedule the interview. If the interview is scheduled more than 1 day after the participant agrees to participate, we will ask their permission to send a reminder text/email/phone call on the day before the interview.

We also asked about other or better means to contact them. These might include being contacted via social media. In that case, we will use the email script (or as close to it as possible if there are space limitations in the social media platform♦s messaging system).

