Randomization. Fifty participants in each study site will be randomized to the intervention or wait-list minimal treatment control group. Assuming 80% retention, this will yield a total sample size of 80 (40 in each site). When assigning participants to treatment/control, we will use urn randomization, an adaptive randomization procedure that ensures approximately equal group sizes while approaching complete randomization.⁹⁴ Adherence to the intervention and supervision of interventionists. Sessions will be conducted in private spaces at our community partner locations according to the guidelines in the treatment manual developed in Aim 2. Facilitators will follow checklists developed for each session and will complete a post-session quality assurance form after each session. All study sessions will be digitally recorded. Study investigators will listen to the first recording of each session and provide feedback to interventionists regarding adherence and quality of administration. Thereafter, study investigators will listen to 20% of all recordings (chosen randomly) and provide feedback as needed. To ensure consistency across study site, investigators will listen to audiotapes and provide feedback for both study sites. Monthly group supervision with interventionists will be conducted by the investigators.

Tracking and retention procedures: As it is common for economically marginalized individuals to move frequently and to be financially unable to maintain consistent phone service, comprehensive tracking information will be collected and updated monthly. This information will include home addresses and phone numbers, but also email addresses, social media account information (e.g., Facebook, Instagram) and contact information for individuals who would know how to reach the participants (e.g., friends, family, health care providers, emergency shelter staff). Participants will also be asked to update contact information at the end of each intervention/assessment session. To increase session attendance, we will offset transportation costs.

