Screening: In person recruitment and screening will be undertaken in areas where participants naturally gather, and thus they will not be asked to present themselves to a research center or other setting that could identify them as participating in an HIV-related research study. Individuals recruited online can access the screening assessment from a private space of their choosing. We will obtain a waiver of written documentation of informed consent for individuals completing the screening survey, consistent with our pilot work. Efforts will be made to ensure that the participant has an opportunity to complete the screening survey privately (e.g., if recruited in a community setting such as a club they will be asked to move to an empty table away from other customers). Screening will be completed anonymously but individuals who screen as eligible will be invited to attend a session to complete a qualitative interview (Aim 1), pilot of the intervention (Aim 2) or baseline assessment (Aim 3) and will be asked to provide contact information.

Participants in the research setting: Individuals participating in the Aim 1 qualitative interviews and aims 2 and 3 intervention groups will be asked to come to VCU or a participating NGO, but steps will be taken to insure that they can preserve their privacy when doing so (e.g., will be immediately escorted to the room where the interview or intervention will occur rather than being asked to wait in a waiting room).

Informed consent: At each stage of the study, study staff will provide a verbal and written description of the study using language comparable with our prior work and approved by the relevant IRBs. Participants will be given an opportunity to keep a blank copy of the informed consent forms which will contain contact information, including phone number and email, for the site PIs. Study personnel will answer any questions participants have. We will stress that participants can decline to answer any question and can withdraw from the study at any time. For the screening survey and Aim 1 qualitative interviews we will collect contact information (e.g., first name, phone #, email address) but will obtain a waiver of written documentation of informed consent, consistent with our pilot work. . We will also collect signed consent forms from participants in the Aim 2 and Aim 3. Signed consent forms will be stored in a locked filing cabinet in the site PI's research space.

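### The Aim 3 consent entry ties signed consent to the first intervention session, which does not fit a wait-list arm and conflicts with other sections; the order of consent, baseline and randomisation is nowhere stated

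*Combined protocol and SAP*

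**What the plan says.** The Consent Groups entry for the Aim 3 intervention asks, at item 5, when, where and how consent is obtained. The answer is "Immediately prior to the first intervention session", followed by "The basics of the process will be provided over the phone prior to participants being scheduled for the first session". The summary table under Consent Process repeats this. That table shows written consent with no waivers requested for this group, and the group does not appear in the Waiver of Documentation of Consent table.

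The design has a delayed arm. Study Procedures, under Randomization, says "Fifty participants in each study site will be randomized to the intervention or wait-list minimal treatment control group". The Aim 3 e-mail script in the same section tells women: "If you are randomly assigned to receive the intervention in 6 months, you will come to three sessions on three different days".

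Other text points to an earlier consent visit. Item 7 of the same Aim 3 entry says "We will contact them within a day or two of them screening eligible and the appointment could be several days after that", and then "Once at the in-person meeting, we will ensure they have at least 15 minutes to decide if they need it". The Risks section (Screening) invites eligible Aim 3 women to a session for the baseline assessment. The Privacy section has eligible women come in for consent and study procedures together.

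**The concern.** Tying consent to the first session works for a single-group pilot, where that session is the first thing that happens. Aim 3 differs in two ways: its first procedure is a baseline assessment, and half of its participants have no session for months.

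If staff followed item 5 literally, controls would be asked for pay stubs, bank statements, HIV test results and pill counts before signing anything, although signed consent is required and no waiver is sought.

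There is also a statistical cost. If women decide after allocation, refusal can depend on arm. Item 6 of the entry says they may still change their minds on arriving for the session, when the arm can already be known. If the decision point also falls at different times in the two arms, the consented groups need not be comparable. The plan promises intent-to-treat analysis but does not say how a woman who was randomised and never consented would be handled.

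**Working it through.** The plan gives no figure to reproduce, so the check sets the sections side by side.

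**Step 1. Literal timeline for a control.** This uses item 5 with the e-mail script's schedule, in which the second questionnaire comes 3 months after the first and the rest follow at 3-month steps.

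| Month | Event in the control arm | Basis |
|---|---|---|
| 0 | Baseline | E-mail script; Risks, Screening |
| about 0 | Randomisation | Implied, since it decides who starts right away; not dated |
| 3 | Second questionnaire | E-mail script |
| 6 | Third questionnaire | E-mail script |
| about 6 | First workshop session, and so consent under item 5 | E-mail script with item 5 |
| 9 | Fourth questionnaire | E-mail script |

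Consent would follow baseline, randomisation and the month-3 assessment. The month-6 assessment falls at about the same time as the workshop, and their order is not given.

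**Step 2. The other assessment clock.** Assessment procedures and measures counts follow-up as 3, 6 and 9 months post-intervention and gives no anchor for the wait-list arm. On that clock the number of follow-ups before consent cannot be fixed. It could be none if months are counted from the controls' own workshop. Randomisation would still come first.

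**Step 3. The immediate arm.** These women attend six sessions starting right away; controls attend three, later. Booking a first session therefore depends on the allocation, so consent just before it would probably follow randomisation here too.

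**Step 4. Items 5 and 7 of the same entry.** Item 7 puts the decision at a meeting within days of screening. For a control, that meeting cannot be a first session 6 months away, so the two items cannot both describe her consent.

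**Step 5. Does another section settle the order?** The Privacy text covers all three aims and does not place consent relative to baseline or randomisation. The Risks text (Informed consent) promises a description of the study at each stage and says that forms are signed in Aims 2 and 3, but not when. Neither settles it.

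**Step 6. Size.** Aim 3 has 50 women per arm, 25 per arm in Richmond, so the rule covers 50 controls. Randomization assumes 80% retention, so overall loss is 20%, and 0.20 × 50 = 10. The plan does not say how much loss falls before month 6. Assuming equal loss by arm, the range runs from 0 (all loss later) to 10 (all loss by then).

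**The case against.** The strongest reply is that nobody planned to consent controls at month 6. No section says so. That reading joins a generic sentence, carried over from the Aim 2 entry, to a delay given only in a recruitment script. Item 7, the Risks section and the Privacy section all point to an early visit, and the Consent Process table only summarises the same entry, so it is not independent support. The Documents section also lists an approved Aim 3 consent form, which is not available here and may state the order.

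Much of this stands. A reader might infer that month-6 consent is the settled plan, and the documents do not support that. Nor do they show that 6-month data would certainly be collected before consent, or that 10 controls would be lost before signing.

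The reply does not remove the problem. Item 5 is the field that answers when consent is taken, and its answer cannot work for a delayed arm. Item 7 is shared template text as well, repeated for the Aim 2 pilot and the interviews with transgender participants, so it is not a deliberate Aim 3 rule either. Even if the consent form is clear, the protocol entry must agree with it.

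**Conclusion.** The point holds as an inconsistency in a basic trial step. The stated Aim 3 consent rule does not fit a wait-list design, it conflicts with item 7 of its own entry and with the Risks and Privacy sections, and no available text orders signed consent, baseline and randomisation in either arm.

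Read literally with the 6-month delay, the rule puts consent for all 50 controls after baseline and randomisation and, on the e-mail script's schedule, after at least one follow-up. The 0 to 10 range is conditional on that literal reading and on the loss assumptions above; it is not a forecast. Early consent may well be what the investigators intend, in which case comparability is not harmed and only the text is wrong. It still needs correcting, because staff could follow item 5 as it stands.

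**What to change.** Amend item 5 of the Aim 3 Consent Groups entry, and its line in the Consent Process table, to state that signed consent is obtained from every participant in both arms at the baseline session, before the baseline assessment and before randomisation. Check that item 7, the Risks and Privacy text and the Aim 3 consent form give the same order.

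The cost is a one-sentence amendment with matching edits. The Risks section already describes a baseline session, so no visit, procedure or participant is added, and the sample size and analysis do not change.
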